2. INTRODUCTION

This statistical analysis plan (SAP) provides the detailed methodology for summary and statistical analyses of the data collected in Study C3421019. This document may modify the plans outlined in the protocol; however, any major modifications of the primary endpoint definition or its analysis will also be reflected in a protocol amendment.

2.1. Modifications to the Analysis Plan Described in the Protocol

None.

2.2. Study Objectives, Endpoints, and Estimands

Туре	Objective	Endpoint	Estimand
Primary Efficacy	To compare the effect of multiple dose levels of PF-06882961 versus placebo on body weight in participants with obesity.	Percent CFB in body weight at End of Treatment.ª	Estimand 1: This estimand is intended to provide a population level estimate of the mean treatment effect (PF-06882961 versus placebo) on a continuous endpoint in all evaluable participants while on treatment
Secondar y (Safety)	To characterize the safety and tolerability of multiple dose levels of PF-06882961 administered to participants with obesity.	 Incidence of treatment emergent AEs [AEs and SAEs], and clinically significant abnormal laboratory, vital signs and ECG parameters. Assessment of mental health as determined by C-SSRS and PHO-9 	There are no defined estimands for these endpoints and they will be analyzed using Pfizer data standards as applicable.
Secondar y (Efficacy)	To compare the effect of multiple dose levels of PF-06882961 versus placebo on additional parameters of body weight in participants with obesity.	 Response as defined by a body weight loss of ≥5% from baseline at End of Treatment.^a 	Estimand 2: This estimand is intended to provide a population level estimate of the odds ratio treatment effect (PF-06882961 versus placebo) on a binary endpoint in all evaluable participants while on treatment.

		•	Cohorts 1 and 2 : Percent CFB in body weight at Weeks 2, 4, 6, 8, 10, 12, 16, 18 and 22. Cohort 3 : Percent CFB in body weight at Weeks 4, 8, 12, 16, 20, 24 and 28.	Estimand 1 as above.
			circumference at End of Treatment.ª	intended to provide a population level estimate of the mean treatment effect (PF-06882961 versus placebo) on a continuous endpoint in all evaluable participants while on treatment.
		•	Absolute CFB in waist-to- hip ratio at End of Treatment.ª	Estimand 4: This estimand will be similar to 3 above.
Secondar y (Efficacy)	To compare the effect of multiple dose levels of PF-06882961 versus placebo on glycemic parameters in participants with obesity.	•	Cohorts 1 and 2 : Absolute CFB in HbA1c at Weeks 16 and 26. Cohort 3 : Absolute CFB in HbA1c at Weeks 16, 24 and 32.	Estimand 5: This estimand will be similar to 3 above.
		•	Absolute CFB in FPG at each planned in-clinic study visit up through the End of Treatment visit. ^b	Estimand 6: This estimand will be similar to 3 above.
Tertiary/ Explorato ry	To compare the effect of multiple dose levels of PF-06882961 versus placebo on body weight in participants with obesity who do not have major protocol deviations.	•	Percent CFB in body weight at each planned in- clinic study visit up through the End of Treatment visit. ^b	Estimand 7: This estimand is intended to provide a population level estimate of the mean treatment effect (PF-06882961 versus placebo) on a continuous endpoint in evaluable participants with no major protocol deviations and while on treatment.
Tertiary/ Explorato ry	To characterize the PK of PF-06882961 in participants with obesity.	•	Trough plasma concentrations of PF-06882961 at time points specified in the SoA for the applicable cohort (see SoA for Cohorts 1 and 2, and SoA for Cohort 3).	There is no defined estimand for this endpoint and this will be analyzed using Pfizer data standards as applicable.
Tertiary/ Explorato ry	To compare the effect of multiple dose levels of PF-06882961 versus placebo on markers of insulin resistance in participants with obesity.	•	Cohorts 1 and 2 : CFB in fasting plasma insulin, HOMA-IR and HOMA-B at Weeks 4, 8, 12, 16, 22 and 26. Cohort 3 : CFB in fasting plasma insulin, HOMA IR and HOMA-B at Weeks 4, 8, 12, 16, 20, 24, 28 and 32.	There are no defined estimands for these endpoints and they will be analyzed using Pfizer data standards as applicable.
Tertiary/	To compare the effect of multiple dose levels of	•	Cohorts 1 and 2: Absolute CFB in waist circumference	Estimand 3: This estimand is defined above.

PFIZER CONFIDENTIAL DMB02-GSOP-RF02 8.0 *Statistical Analysis Plan Template* TMF Doc ID: 98.03 Page 9 of 61

Explorato ry	PF-06882961 versus placebo on additional parameters of body weight in participants with obesity.	at Weeks 2, 4, 6, 8, 10, 12, 16, 18 and 22. • Cohort 3: Percent CFB in body weight at Weeks 4, 8, 12, 16, 20, 24 and 28. • Cohorts 1 and 2: Absolute CFB in waist-to-hip ratio at Weeks 2, 4, 6, 8, 10, 12, 16, 18 and 22. • Cohort 3: Percent CFB in body weight at Weeks 4, 8, 12, 16, 20, 24 and 28.
	To compare the effect of multiple dose levels of PF-06882961 versus placebo on glycemic category in participants with obesity.	 Shift from baseline in glycemic category (normoglycemia, pre-diabetes, or T2DM) at End of Treatment.^a There are no defined estimands for these endpoints and they will be analyzed using Pfizer data standards as applicable.
	To compare the effect of multiple dose levels of PF-06882961 versus placebo on blood pressure (BP) and lipid levels in participants with obesity.	 CFB in systolic and diastolic BP at each planned in-clinic study visit up through the End of Treatment visit. Cohorts 1 and 2: CFB in lipid parameters at Weeks 4, 8, 12, 16, 22 and 26. Cohort 3: CFB in lipid parameters at Weeks 4, 8, 12, 16, 20, 24, 28 and 32.
	To compare the effect of multiple dose levels of PF-06882961 versus placebo on PCOAs in participants with obesity.	 Cohorts 1 and 2: CFB in SF-36v2[®] subscales and summary scores at Weeks 16 and 26. Cohort 3: CFB in SF- 36v2[®] subscales and summary scores at Weeks 16, 24 and 32.
	To compare the effect of multiple dose levels of PF-06882961 versus placebo on PCOAs in participants with obesity (US sites only).	 Cohorts 1 and 2: CFB in Eating-Related Factors Daily Diary at Weeks 4, 8, 12, 16, 22 and 26. Cohort 3: CFB in Eating-Related Factors Daily Diary at Weeks 4, 8, 12, 16, 20, 24, 28 and 32. CFB in PGI-S at each planned in-clinic study visit up through the End of Treatment visit.^b Cohorts 1 and 2: CFB in PROMIS[®] Fatigue at Weeks 16 and 26. Cohorts 1 and 2: CFB in PROMIS[®] Fatigue at Weeks 16, 24 and 32. Cohorts 1 and 2: CFB in PROMIS[®] Fatigue at Weeks 16, 24 and 32. Cohorts 1 and 2: CFB in PROMIS[®] Physical

PFIZER CONFIDENTIAL DMB02-GSOP-RF02 8.0 *Statistical Analysis Plan Template* TMF Doc ID: 98.03 Page 10 of 61

	 Function at Weeks 16 and 26. Cohort 3: CFB in PROMIS® Physical Function at Weeks 16, 24 and 32. Cohorts 1 and 2: CFB in IWQOL-Lite-CT® at Weeks 16 and 26. Cohort 3: CFB in IWQOL Lite-CT© at Weeks 16, 24 and 32. Cohorts 1 and 2: PGI-C at Weeks 4, 16 and 26. Cohort 3: PGI-C at Weeks 4, 16, 24 and 32.
Note: For all endpoints baseline is define	ed as the result closest prior to dosing at V3 (Day 1)

a. End of Treatment defined as Week 26 for Cohorts 1 and 2, and as Week 32 for Cohort 3.

b. For Cohorts 1 and 2, this includes Weeks 2, 4, 6, 8, 10, 12, 16, 18, 22 and 26; for Cohort 3, this includes Weeks 4, 8, 12, 16, 20, 24, 28 and 32.

2.2.1. Primary Estimand(s)

The primary estimand (Estimand 1) will be the population average treatment effect on the percent change from baseline (CFB) in body weight at End of Treatment of PF-06882961 (danuglipron) compared to placebo in all evaluable participants while on treatment. For Cohorts 1 and 2, End of Treatment is defined as Week 26. For Cohort 3, End of Treatment is defined as Week 32. This reflects a combination of the 'Hypothetical' and 'While on treatment' strategies as outlined in the ICH-E9 (R1) guidance.¹ It includes the following 4 attributes:

- Population: Defined by the inclusion and exclusion criteria to reflect participants with obesity
- Variable: Percent change from baseline in body weight at End of Treatment
- Intercurrent events: All data after an intercurrent event of discontinuation of investigational product (IP) will be censored
- Population-level summary: Mean percent change from baseline in each danuglipron arm compared to placebo

2.2.2. Secondary Estimand(s)

2.2.2.1. Estimand related to achieving Body Weight loss ≥5% at End of Treatment

A secondary estimand (Estimand 2) will be the population odds ratio of the treatment effect of achieving a body weight loss \geq 5% from baseline at End of Treatment of PF-06882961 (danuglipron) compared to placebo in all evaluable participants while on treatment. This reflects a combination of the 'Hypothetical' and 'While on treatment' strategies as outlined in the ICH-E9 (R1) guidance.¹ It includes the following 4 attributes:

Population: Defined by the inclusion and exclusion criteria to reflect participants with obesity

PFIZER CONFIDENTIAL DMB02-GSOP-RF02 8.0 *Statistical Analysis Plan Template* TMF Doc ID: 98.03 Page 11 of 61

- Variable: Response as defined by a body weight loss of ≥5% from baseline at End of Treatment
- Intercurrent events: All data after an intercurrent event of discontinuation of investigational product (IP) will be censored. Missing or censored values at End of Treatment will be imputed (assuming missing at random [MAR]) to determine a response classification.
- Population-level summary: Odds ratio for a response between danuglipron (each arm considered separately) and placebo

2.2.2.2. Estimands related to Waist Circumference at End of Treatment

Estimand 3 is similar to Estimand 1, except the population average treatment effect is on the absolute CFB in waist circumference at End of Treatment. The population based treatment effect will be the mean CFB in each PF-06882961 (danuglipron) arm compared to placebo.

2.2.2.3. Estimands related to Waist-to-hip ratio, HbA1c and Fasting Plasma Glucose

Estimands 4, 5 and 6 will utilize the same approach as Estimand 3 (Section 2.2.2.2) for the associated endpoint(s).

2.2.3. Additional Estimand(s)

An additional exploratory estimand (Estimand 7) will be analyzed, which will be the population average treatment effect on the percent CFB in body weight at End of Treatment of PF-06882961 (danuglipron) compared to placebo in evaluable participants with no major protocol deviations and while on treatment. This reflects a combination of the 'Hypothetical', 'While on treatment' and 'Principal stratum' strategies as outlined in the ICH-E9 (R1) guidance.¹

It includes the following 4 attributes:

- Population: Defined by the inclusion and exclusion criteria to reflect participants with obesity who do not have major protocol deviations
- Variable: Percent change from baseline in body weight at End of Treatment
- Intercurrent events: All data after an intercurrent event of discontinuation of investigational product (IP) will be censored
- Population-level summary: Mean percent change from baseline in each danuglipron arm compared to placebo

2.3. Study Design

This is a Phase 2b, multicenter, randomized, double-blind, placebo-controlled, parallel group, study to assess efficacy, safety, tolerability and PK of twice daily oral administration of PF-06882961 (danuglipron) in adult participants with obesity. There are 3 Cohorts included in the study: Cohort 1 under the original protocol, Cohort 2 added under Amendment 1, and Cohort 3 added under Amendment 2.

PFIZER CONFIDENTIAL DMB02-GSOP-RF02 8.0 *Statistical Analysis Plan Template* TMF Doc ID: 98.03 Page 12 of 61 For all cohorts, following the initial screening period to confirm eligibility (up to 4 weeks), screening continues with a 2-week placebo run-in period which will be single-blinded (participant). Eligible participants who maintain acceptable compliance during the run-in period are randomized on Day 1 to double-blinded study intervention.

For participants in Cohorts 1 and 2, the total duration of dosing with double-blinded study intervention is 26 weeks, followed by an approximate 4-week follow-up. The total duration of participation in this study for the participants in Cohorts 1 and 2 is approximately 32 weeks, including the 2-week single-blind run-in period, but excluding the initial screening period.

For Cohort 3, added under protocol Amendment 2, participants will be randomized to placebo or 1 of 3 PF-06882961 (danuglipron) arms with 4-week dose titration steps. The total duration of dosing with double-blinded study intervention is 32 weeks, followed by an approximate 4-week follow-up. The total duration of study participation for participants in Cohort 3 is approximately 38 weeks, including the 2-week single-blind run-in period, but excluding the initial screening period.

All dosing regimens for all cohorts include dose titration to enhance tolerability of PF-06882961 (danuglipron), where the dose level is increased at set intervals of 1, 2 or 4 weeks until a target dose is achieved. For all cohorts, dosing is to occur with food twice daily. For the 5 1-week titration PF-06882961 (danuglipron) groups in Cohort 1, the target dose levels for each of the arms are 40 mg BID, 80 mg BID, 120 mg BID, 160 mg BID, and 200 mg BID, with titration from a starting dose of 10 mg BID, and up to 10 weeks of the dosing duration used for titration. For the 3 2-week titration PF-06882961 (danuglipron) groups in Cohorts 1 and 2, target dose levels for each of the arms are 120 mg BID, 160 mg BID, and 200 mg BID, with titration from a starting dose of 10 mg BID, and up to 20 weeks used for titration. Both Cohorts 1 and 2 also include a placebo arm. For Cohort 3, participants will be enrolled into 4 study arms, and target dose levels are placebo and PF-06882961 (danuglipron) doses of 80 mg BID, 140 mg BID, and 200 mg BID. For Cohort 3, titration will occur at 4-week intervals from a starting dose of 10 mg BID, and up to 20 weeks will be used for titration to reach the target dose.

There will be total of approximately 581 participants across all 3 cohorts of this study. In Cohort 1, approximately 420 participants (approximately 60 in each of the placebo and 5 1-week titration PF-06882961 (danuglipron) arms and approximately 20 participants in each of the 3 2-week titration arms) were randomized. All dosing arms, including placebo, were enrolled simultaneously in Cohort 1. Subsequently, in Cohort 2, approximately 49 additional participants were randomized to the placebo and 2-week titration arms (approximately 7 in the placebo and approximately 14 in each of the 3 2-week titration arms). Combining Cohorts 1 and 2, there are a total of approximately 469 participants randomized (approximately 67 in the placebo, approximately 60 each of the 5 1-week titration arms and approximately 34 in each of the 3 2-week titration arms). In Cohort 3, approximately 112 participants will be randomized to 4 additional study arms (approximately 16 in the placebo and approximately 32 in each of 3 PF-06882961 (danuglipron) arms with 4-week titration steps).

Eligible participants in the Cohort 1 will be randomized to double-blinded study intervention in 1 of 9 arms in a 3:3:3:3:3:1:1:1 ratio (placebo: 5 standard titration danuglipron arms: 3 2-week titration arms). Eligible participants in Cohort 2 will be randomized to double-blinded study intervention in 1 of 4 arms in a 1:2:2:2 ratio (1 placebo: 3 2-week titration arms). Similarly for Cohort 3, eligible participants will be randomized to double-blinded study PFIZER CONFIDENTIAL DMB02-GSOP-RF02 8.0 Statistical Analysis Plan Template

IB02-GSOP-RF02 8.0 *Statistical Analysis Plan Templ*a TMF Doc ID: 98.03 Page 13 of 61 intervention in 1 of 4 arms in a 1:2:2:2 ratio (1 placebo: 3 4-week titration arms). Randomization is stratified according to biological gender (female versus male), as both tolerability and efficacy may be different between men and women. This stratification is intended to balance the numbers of participants of either gender across treatment arms. In addition, no more than approximately 70% of the trial population will consist of 1 gender, in order to permit adequate representation of both men and women in the trial population.

Figure 1: Overall Study Schema for Cohorts 1 and 2

Figure 4: Titration Schema for Cohort 3

3. ENDPOINTS AND BASELINE VARIABLES: DEFINITIONS AND CONVENTIONS

For all endpoints, unless otherwise specified below, baseline is defined as the result closest prior to dosing at V3 (Day 1).

The "End of Treatment" definition is applied at the endpoint level (not the subject-level) and is defined for relevant endpoints as Week 26 for Cohorts 1 & 2, and as Week 32 for Cohort 3.

3.1. Primary Endpoint(s)

• Percent change from baseline in body weight at End of Treatment.

The average of the duplicate body weight readings collected at each assessment time will be calculated prior to summaries/analysis. If one of the two duplicates are missing, the non-PFIZER CONFIDENTIAL

DMB02-GSOP-RF02 8.0 Statistical Analysis Plan Template TMF Doc ID: 98.03 Page 15 of 61 missing value will be used, and missing values will not be imputed. Both the absolute change and percent change from baseline in body weight will be calculated.

For the MMRM model, all body weight values (including baseline) will be log_e-transformed prior to analysis (i.e. the outcome in the model will be the difference of the log_e absolute value at the time point of interest minus the log_e baseline). All LSMeans and LSMean differences (including confidence intervals) will be back-transformed to obtain the ratio to baseline or placebo (as applicable). The percent change from baseline or percent difference to placebo (as applicable) will then be calculated as follows:

Percent change = 100^{*} (back-transformed LSMean – 1)

For descriptive summaries, percentage change from baseline will be calculated as the End of Treatment measurement minus the baseline value divided by the baseline value multiplied by 100.

The absolute change from baseline in body weight at End of Treatment will also be calculated for additional reporting.

3.2. Secondary Endpoint(s)

3.2.1. Efficacy Endpoint(s)

• Response as defined by a body weight loss of ≥5% from baseline at End of Treatment

This endpoint will have two levels: 'Response' and 'Non-response'. The former will be based on participants having a body weight loss of \geq 5% from baseline at End of Treatment, otherwise participants with a loss of <5% will be classed as having a 'Non-response'. Participants with an intercurrent event of discontinuation of IP prior to, or on, the End of Treatment week will have their End of Treatment value censored (if not missing). Missing or censored values at End of Treatment will be imputed as described in Section 5.3. Percent change will be calculated as described in Section 3.1 (based on the descriptive summaries approach).

- Percent CFB in body weight at:
 - \circ $\,$ Weeks 2, 4, 6, 8, 10, 12, 16, 18 and 22 for Cohorts 1 and 2 $\,$
 - Weeks 4, 8, 12, 16, 20, 24 and 28 for Cohort 3.

Data will be analysed on the natural log scale and the percent change from baseline will be calculated as described in Section 3.1.

• Absolute CFB in waist circumference at End of Treatment.

The average of the triplicate waist measurements collected at each assessment time will be calculated prior to summaries/analysis. If any of the triplicates are missing, the non-missing value(s) will be used, and missing values will not be imputed.

• Absolute CFB in waist-to-hip ratio at End of Treatment.

PFIZER CONFIDENTIAL DMB02-GSOP-RF02 8.0 Statistical Analysis Plan Template TMF Doc ID: 98.03 Page 16 of 61 The average of the triplicate waist and hip measurements collected at each assessment time will be calculated prior to calculating the waist-to-hip ratio at each assessment time. If any of the triplicates are missing, the non-missing value(s) will be used, and missing values will not be imputed.

- Absolute CFB in HbA1c at:
 - Weeks 16 and 26 for Cohorts 1 and 2.
 - Weeks 16, 24 and 32 for Cohort 3.
- Absolute CFB in Fasting Plasma Glucose (FPG) at each planned in-clinic study visit up through the End of Treatment visit

3.2.2. Safety Endpoint(s)

3.2.2.1. Adverse Event

If an adverse event has a start time of 00:00 and a start date that is equal to the date of first administration of IP, the adverse event start time will be imputed with the time of the first dose of administration of IP.

If an adverse event has an end time of 00:00 then the end time will be imputed as 23:59.

An adverse event is considered treatment emergent (TEAE) relative to a given treatment if the event starts during the effective duration of treatment (i.e. starting on or after the first dose but before the last dose plus lag time).

The effective duration of treatment is determined by the lag time. Any event occurring within the lag time, whether this occurs during a break in treatment or at the end of treatment, is attributed to the corresponding treatment period. The lag time is defined by the Pfizer Standard of 365 days post last dose of IP.

Adverse events occurring during the placebo run-in period (i.e. starting from Day -14, inclusive, up to and before the first dose of active treatment on Day 1) will be considered non-treatment emergent.

A 3-tier approach will be used to summarize TEAEs. Under this approach, TEAEs are classified into 1 of 3 tiers. Different analyses will be performed for different tiers (see Section 6.3.1.

Tier 1 events: These are prespecified events of clinical importance and are maintained in a list in the product's Safety Review Plan.

Tier 2 events: These are events that are not tier 1 but are "common." A Medical Dictionary for Regulatory Activities (MedDRA) preferred term (PT) is defined as a Tier 2 event if there are at least 5% of participants reporting the event in any of the standard titration or placebo groups or at least 2 participants reporting the event in any of the slow titration groups.

Tier 3 events: These are events that are neither Tier 1 nor Tier 2 events.

PFIZER CONFIDENTIAL DMB02-GSOP-RF02 8.0 *Statistical Analysis Plan Template* TMF Doc ID: 98.03 Page 17 of 61

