4. STUDY DESIGN

4.1. Overall Design

This Phase 2b, multicenter, randomized, double-blind, placebo-controlled, parallel group, study will assess efficacy, safety, tolerability and PK of twice daily oral administration of PF-06882961 in adult participants with obesity. There are 3 Cohorts included in the study: Cohort 1 under the original protocol, Cohort 2 added under Amendment 1, and Cohort 3 added under Amendment 2, as described below.

For all cohorts, following the initial screening period to confirm eligibility (up to 4 weeks), screening continues with a 2-week placebo run-in period which will be single-blinded (participant). Eligible participants who maintain acceptable compliance during the run-in period are randomized on Day 1 to double-blinded study intervention.

This study was initially designed with a 2-part double-blinded treatment phase, as the 16-week dosing duration of Part A was supported by the nonclinical toxicology data available at the time of the original protocol finalization, and dosing in Part B over Weeks 17-26 was contingent on availability of supportive nonclinical data from a 9-month toxicology study in monkeys (Study CCI) that was ongoing at that time, and is now completed. For Cohort 1, participants were randomized into 9 arms: a placebo arm, 5 arms with 1-week titration steps (also referred to as standard titration in previous protocol versions), and 3 arms with 2-week titration steps (also referred to as slow titration in previous protocol versions). Protocol Amendment 1 added Cohort 2 where additional participants were randomized to the placebo and the 3 arms with 2-week titration steps. All SoA activities are the same for Cohort 2 as for the original cohort (Cohort 1) of randomized participants. Part B was approved before any participant reached the end of Part A, and participants in both Cohorts 1 and 2 were able to proceed directly from Part A to Part B. Accordingly, the primary endpoint for Cohorts 1 and 2 is based on End of Treatment defined as Week 26. For participants in Cohorts 1 and 2, the total duration of dosing with double-blinded study intervention is 26 weeks, followed by an approximate 4-week follow-up. The total duration of participation in this study for the participants in Cohorts 1 and 2 is approximately 32 weeks, including the 2-week single-blind run-in period, but excluding the initial screening period.

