6.3.1. Adverse Events

Adverse events (Tier 1, 2 and 3 AEs as described in Section 3.2.2.1) will be summarized by treatment group and overall and in accordance with sponsor reporting standards using the safety analysis set defined in Section 4. The adverse events (AEs) will be sorted in descending frequency within a system organ class.

Incidence and severity of treatment emergent adverse event (TEAE) tables will additionally be produced ('All causality' and 'Treatment related', separately) to summarise the total number of adverse events by preferred term, which will be reported by treatment group and overall.

The following tables and figures related to TEAEs classed as Tier 1 or 2 will be ordered in descending point estimate of risk difference within System Organ Class. If two or more events have the same frequency, they will be sorted alphabetically by preferred term.

TEAEs classed as Tier 1 events will be tabulated by treatment group. Number of participants and percent will be presented, along with the risk difference between each treatment group of danuglipron and placebo. 95% confidence intervals and p-values will also be presented for the comparison. No adjustment for multiplicity will be used.

Tier 1 TEAEs will also be presented graphically. The TEAEs will be presented in a two-panel plot, the left panel will give the proportions of TEAEs observed in a treatment group of danuglipron and separately placebo while the right panel will display the 95% confidence interval for the risk differences for each TEAE. A vertical line corresponding to the value of 0 will be added to the right-hand plot. For the graphical display for tier 1 events, a column containing the p-value for each event will be added to the right-hand side of the forest plot in the right panel. Each panel will be paged by treatment group of danuglipron.

TEAEs classed as Tier 2 events will be summarised and graphically presented similar to Tier 1 events, but no p-values will be presented. No adjustments for multiplicity will also be used.

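### The Tier 2 adverse-event rule was not extended to the Cohort 3 4-week arms, so no count in those arms can by itself make a preferred term Tier 2

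*SAP*

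**What the plan says.** SAP 3.2.2.1 sorts treatment-emergent adverse events into three tiers. A preferred term that is not Tier 1 becomes Tier 2 by one of two routes: a threshold of 5% for some groups, or a count of two for others. The wording that assigns groups to the routes is "standard titration or placebo groups or at least 2 participants reporting the event in any of the slow titration groups". Everything else is Tier 3.

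The SAP does not define standard or slow. Protocol 4.1 does. It explains that standard was the former name for the five 1-week arms of Cohort 1, and it describes the remaining active arms of that cohort as "3 arms with 2-week titration steps (also referred to as slow titration in previous protocol versions"). Both labels predate Cohort 3, and Protocol Amendment 2 replaced them with the number of weeks per step.

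Tier 2 status decides which comparison is displayed. SAP 6.3.1 gives Tier 1 events a risk difference against placebo with a 95% confidence interval and p-value, plus a two-panel plot, and then says "TEAEs classed as Tier 2 events will be summarised and graphically presented similar to Tier 1 events, but no p-values will be presented".

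Cohort 3 is planned with "approximately 16 in the placebo and approximately 32 in each of 3 PF-06882961 (danuglipron) arms with 4-week titration steps". SAP 5.2 gives its arms their own 4-week labels and puts them in tables separate from Cohorts 1 and 2.

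**The concern.** Cohort 3 was added to characterise tolerability and efficacy with 4-week titration steps. The rule that selects ordinary (non-Tier 1) events for a comparison with placebo names every treatment group in the study except the three 4-week arms. SAP version 2 was written to take in Cohorts 2 and 3, and its change log records updated titration labels, but this sentence kept the old ones. SAP 5.1 also keeps them.

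At stake is whether an event that is frequent on a 4-week regimen receives a risk difference and interval. Under the written rule it does so only if some other group, possibly only the small Cohort 3 placebo arm, happens to trigger Tier 2.

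**Working it through.** **Inputs.** Planned sizes from SAP 2.3: 60 in each 1-week arm, 34 in each 2-week arm and 67 on placebo (Cohorts 1 and 2 combined); 32 in each 4-week arm and 16 on placebo (Cohort 3). Protocol 9.2 allows Cohort 3 to grow to about 140. The event rates below are assumptions, because the documents give none by preferred term.

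**Step 1: reproduce the Cohort 3 sizes.** SAP 2.3 states "intervention in 1 of 4 arms in a 1:2:2:2 ratio (1 placebo: 3 4-week titration arms"). With 112 participants, 112 × 1/7 = 16 and 112 × 2/7 = 32, as planned. With 140, the sizes are 20 and 40.

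**Step 2: smallest count that makes a term Tier 2, as written.**

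| Group | n | Limb that applies | Smallest count |
|---|---|---|---|
| 1-week arm | 60 | at least 5% | 3 (5.0%) |
| Placebo, Cohorts 1 and 2 | 67 | at least 5% | 4 (6.0%; 3/67 = 4.5% fails) |
| 2-week arm | 34 | at least 2 participants | 2 (5.9%) |
| Placebo, Cohort 3 | 16 | at least 5% | 1 (6.25%) |
| 4-week arm | 32 | none | no count qualifies |

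If the 4-week arms were in the 2-participant limb, the trigger would be 2/32 = 6.25%, in line with the 2-week arms.

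**Step 3: tiers assigned within Cohort 3.** Only the placebo arm can then trigger, and one event is enough. With placebo rate p0, the probability is 1 − (1 − p0)^16:

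- p0 = 0%: 0%
- p0 = 1%: 1 − 0.99^16 = 14.9%
- p0 = 2%: 1 − 0.98^16 = 27.6%
- p0 = 5%: 1 − 0.95^16 = 56.0%

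The rate in the 4-week arms does not enter this formula.

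With the 4-week arms added to the 2-participant limb, their own contribution at rate p is 1 − [P(Bin(32, p) ≤ 1)]^3:

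- p = 2%: 1 − 0.866^3 = 35%
- p = 5%: 1 − 0.520^3 = 86%
- p = 10%: 1 − 0.156^3 = 99.6%

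The placebo limb can only raise these.

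**Step 4: tiers assigned study-wide.** The 1-week and 2-week arms can then trigger Tier 2 for the whole study. If the event has the same rate p in all of them, and placebo is ignored, the probability is 1 − [P(Bin(60, p) ≤ 2)]^5 × [P(Bin(34, p) ≤ 1)]^3:

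- p = 5%: 1 − 0.417^5 × 0.488^3 = 1 − 0.0127 × 0.116 = 99.9%
- p = 10%: above 99.9%

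An event that is about as common on the faster regimens is therefore picked up anyway.

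**Step 5: what SAP 6.3.1 shows regardless of tier.** It tabulates events exceeding 5% in any treatment arm, split by titration step. At n = 32 that means 2 participants (6.25%), the same count as the added limb. At n = 40, 2 participants are exactly 5.0%, so 3 are needed to exceed 5%. These are incidence tables; no risk difference or interval is specified for them.

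**The case against.** A reader might infer that the rule conceals drug-related events in Cohort 3. The documents do not support that. SAP 6.3.1 summarises all tiers by treatment group, gives incidence and severity by preferred term, and tabulates terms above 5% in Cohort 3 and in any arm. SAP 6.6.2 tabulates discontinuations of study drug due to adverse events by preferred term. Nausea, vomiting and diarrhoea have tier-independent displays in SAP 6.3.1.1 to 6.3.1.4, including forest plots of incidence with 95% intervals, and gastrointestinal discontinuations are covered in 6.3.1.5. A risk difference could also be worked out by hand from the printed counts. All of this stands, and it limits the loss to one comparative display.

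A reader might also take the 0% to 56% range as the plan's actual performance. It holds only if tiers are assigned within Cohort 3, and the SAP does not say so. Section 5.2 separates tables, not necessarily tier assignment, and the 5% incidence rule in 6.3.1 selects terms by a union across cohorts. On a study-wide reading, most common class effects would already be Tier 2. That stands too, but a term peculiar to 4-week titration, to the 140 mg dose or to the longer 32-week treatment could still be missed.

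A third inference is that one event in 16 triggering Tier 2 is an error. It is not: 6.25% meets the stated 5% threshold.

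Slow could be read loosely to include the 4-week arms, but the protocol's definition is against it. Prespecified Tier 1 events get their comparison at any frequency; that list is in the Safety Review Plan, which is not among the documents, so the number of terms affected cannot be stated. Finally, SAP 6.3.1 calls the safety analysis exploratory and the intervals a screening aid. That lowers the stakes, but the screen should still cover the arms being screened.

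**Conclusion.** The gap is real and limited. As written, the 4-week arms contribute nothing to Tier 2 selection at any event rate, while 2-week arms of almost the same size qualify with 2 participants. The consequence is the absence of the Tier 2 risk difference, 95% interval and two-panel plot for some events; their incidence is still reported.

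The size depends on a choice the SAP leaves open. Assigned within Cohort 3, an event at 10% in each 4-week arm is selected with the Step 3 placebo-driven probabilities instead of at least 99.6%. Assigned study-wide, the loss is confined to events not already common in the Cohort 1 and 2 groups.

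These figures assume the planned arm sizes, independent participants, equal rates across the three 4-week arms, and a Cohort 3 placebo group kept separate and no larger than 20. At 21, one event is 4.8% and no longer qualifies. No efficacy analysis is affected. The rule should be corrected before unblinding, so that the choice of events to compare is not made after seeing the data.

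**What to change.** In SAP 3.2.2.1, replace the standard and slow labels with 1-week and 2-week, add the 4-week titration groups to the limb requiring at least 2 participants, and state whether tiers are assigned separately for each reporting set (Cohorts 1 and 2; Cohort 3) or once across the study. Update the same labels in SAP 5.1 for consistency.

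A minimum count for the small Cohort 3 placebo arm is optional. It would be a preference about noise, not a correction.

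The cost is one sentence in the SAP and a line of tier-assignment code. The Cohort 3 Tier 2 tables become slightly longer.
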